13.2 General Aspects of Analysis

Data from all enrolled patients will be summarized, but analysis of each objective will account for the completeness of the data in the context of addressing the objective. In particular, patients contributing to objectives that are modeling HCU-based outcomes should have provided a minimal amount of information to ensure that HCU data has been made available. This can be accomplished through the completion of monthly and triggered surveys or by sharing EHR information through the study app or via sites. Complete device data should be available for all patients. Patients should have regularly transmitted CareLink data throughout follow-up. If no device data or limited device data is available from a patient, that patient will need to be either excluded from analysis or follow-up will need to be limited to the period of time up until device data is not available.

For patients that enroll at the time of ICM implant, all follow-up data will be analyzed from the time of implant if the patient completes all baseline enrollment tasks within 7 days of the ICM implant. Baseline enrollment tasks include enrollment, signing their consent, and completing all baseline survey questionnaires (patient profile, medical history, medication history, EQ-5D-5L, AFEQT). For patients that are enrolled more than 7 days after the ICM implant or that complete enrollment tasks more than 7 days post-implant, follow-up will begin when the patient has completed electronic consent.

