13.3.2 Determination of Subjects/Data for Analysis

[figure not shown]
All subjects enrolled in the study that have successfully installed the app and consented will be included in the primary objective analysis.

[figure not shown]
DEFINE AFib Clinical Investigation Plan Medtronic Version 4.0 (29JUL2022) Page 37 of 48

DEFINE AFib Clinical Investigation Plan Medtronic Version 4.0 (29JUL2022) Page 38 of 48

DEFINE AFib Clinical Investigation Plan Medtronic Page 39 of 48 Version 4.0 (29JUL2022)

DEFINE AFib Clinical Investigation Plan Version 4.0 (29JUL2022) Page 41 of 48 Medtronic

14. Ethics

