iOS	iPhone Operating System (Apple's mobile operating system developed and distributed by Apple Inc. required for use of it's devices).			
IRB	Institutional Review Board			
LMM	Linear mixed model			
MDT	Medtronic			
ML	Machine Learning			
NPV	Negative predictive value			
PPV	Positive predictive value			
QoL	Quality of Life			
RDC	Remote data capture			
SAE	Serious Adverse Event			
SAP	Statistical Analysis Plan			
SME	Subject- Matter Expert			
TIA	Transient Ischemic Attack			
WAIC	Widely Applicable Information Criterion / Watanabe-Akaike Information Criterion			

Introduction 3.

This Statistical Analysis Plan (SAP) has been designed to document, before data are analyzed, the rationale for the study design, and the planned analyses that will be included in study reports. This SAP

Revision [2.0]

Page 4 of 25

does not limit the analysis in reports. Additional analysis of the study data beyond this plan may be needed. This SAP is developed for the DEFINE AFib study, based on the Clinical Investigation Plan (CIP) version 4 dated July 29, 2022.

Atrial fibrillation (AF) is the most frequent clinically significant cardiac arrhythmia. When diagnosed clinically, AF is associated with increased risk for stroke, heart failure (HF), cardiovascular (CV) morbidity and mortality. It is also a major contributor to the costs of health care. The prevalence of AF is predicted to rise significantly in the coming years due to the aging of the population and growing frequency of other AF risk factors. Considering the rising burden and clinical sequalae of AF, strategies that enable early detection and appropriate clinical management are needed.

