7.1.3 Analysis Sets

All patients who enroll and successfully install the study app will be included in the full analysis set. Additional data inclusion/exclusion constraints specific to an objective are specified within the analysis methods.

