7.2 General Methodology

Data from all enrolled patients will be summarized, but analysis of each objective will account for the completeness of the data in the context of addressing the objective. In particular, patients contributing to objectives that are modeling HCU-based outcomes should have provided a minimal amount of

DEFINE AFib Statistical Analysis Plan Form Medtronic Revision [2.0] Page 11 of 25

information to ensure that HCU data has been made available. This can be accomplished through the completion of monthly and triggered surveys or by sharing EHR information through the study app or via sites. Complete device data should be available for all patients. Patients should have regularly transmitted CareLink data throughout follow-up. If no device data or limited device data is available from a patient, that patient will need to be either excluded from analysis or follow-up will need to be limited to the period of time up until device data is not available.

For patients who enroll at the time of LINQ ICM implant, all follow-up data will be analyzed from the time of implant, if the patient completes all baseline enrollment tasks within 7 days of the LINQ ICM implant. Baseline enrollment tasks include enrollment, signing their consent, and completing all baseline survey questionnaires (patient profile, medical history, medication history, EQ-5D-5L, AFEQT). For patients who are enrolled more than 7 days after the LINQ ICM implant or who completed enrollment tasks more than 7 days post-implant, follow-up will begin when all baseline enrollment tasks have completed.

The final data analysis will be performed by a Medtronic statistician or designee. The timing of the final analysis will be determined during the interim analysis (see Section 7.8). Any change to the data analysis methods described in the protocol will require an amendment only if it changes a principal feature of the protocol. Any other change to the data analysis methods described in the protocol, and the justification for making the change, will be described in the clinical study report.

7.3 **Center Pooling**

[figure not shown]
The primary objective of this study is to develop risk prediction models and not to compare two arms via a hypothesis testing. Thus, poolability analysis will not be performed in this study. However, the following will be done to reduce the effect of possible heterogeneity across sites:

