After all models have been trained and tuned, all final models (i.e. for each clinical endpoint and prediction modeling strategy) will be fitted to the testing dataset resulting in a prediction of each patient's individual probabilities of having the clinical event in the predictive window (i.e. between t+l and t+l+w). More specifically, all models will generate risk prediction (for the clinical event they were designed to predict) for each patient at each day (starting at the bth). The true binary values and the corresponding prediction risk scores will be used to compute the area under the receiver operating characteristic (AUROC), sensitivity, specificity, negative predictive value (NPV) and positive predictive value (PPV). Bootstrapping will be used to compute 95% CIs for these performance metrics.

For each outcome, the performance of the risk prediction models will be presented in contrast to the performance of comparable clinical practices. However, as a guideline, the following scale might be used to help choose the adjective to refer the performance of each model:

AUROC ≤ 0.5: fail

DEFINE AFib Statistical Analysis Plan Form Medtronic Revision [2.0] Page 17 of 25

0.5 < AUROC ≤ 0.6: poor

0.6 < AUROC ≤ 0.7: fair

[figure not shown]
0.7 < AUROC ≤ 0.8: good

[figure not shown]
0.8 < AUROC ≤ 0.9: great

[figure not shown]
AUROC > 0.9: excellent

[figure not shown]
Determination of Subjects/Data for Analysis

Subjects in the full analysis set who have completed all enrollment surveys will be included in the primary objective analysis. Subject follow up might be limited by lack of device information.

[figure not shown]

[figure not shown]

DEFINE AFib Statistical Analysis Plan Form Medtronic Page 20 of 25 Revision [2.0]

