7.12 Changes to Planned Analysis

This version of the SAP is updated to reflect changes in the CIP from version 3 to version 4. Most of the CIP changes had to do with clarifications around the deployment of patient surveys, which have also been updated in this SAP. Changes in the inclusion criteria and descriptions of study objectives have

Revision [2.0]

Page 24 of 25

also been updated in this SAP. There have been no direct changes in the proposed analyses of study objectives. There was a delay in the timing of the interim analysis, which is discussed in Section 7.8.

8. Validation Requirements

All programs written to execute the analyses in this SAP will pass through at least Level II validation

9. References

- 2. Catling, F.J.R., & Wolff, A. H. (2020). Temporal convolutional networks allows early prediction of events in critical care. *Journal of the American Medical Informatics Association*, 27(3), 355-365

DEFINE AFib Statistical Analysis Plan Form Medtronic Revision [2.0] Page 25 of 25

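### The SAP and CIP v4 define the primary analysis population, and the start of follow-up for later enrollees, in incompatible ways

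*SAP*

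**What the plan says.** **Population.** SAP 7.1.3 defines the full analysis set broadly: "All patients who enroll and successfully install the study app will be included in the full analysis set". It lets individual objectives add constraints. SAP 7.9.1 then adds one for the primary objective: "Subjects in the full analysis set who have completed all enrollment surveys will be included in the primary objective analysis". CIP 13.3.2 defines the population for the same objective without it: "All subjects enrolled in the study that have successfully installed the app and consented will be included in the primary objective analysis".

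**Time zero.** CIP 13.2 and SAP 7.2 agree that follow-up runs from implant when a patient enrols at implant and completes every baseline task within 7 days. Both list the same tasks: enrollment, consent and the baseline questionnaires (patient profile, medical history, medication history, EQ-5D-5L, AFEQT). For everyone else they part. In the SAP, "follow-up will begin when all baseline enrollment tasks have completed". In the CIP, "follow-up will begin when the patient has completed electronic consent".

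**Claimed alignment.** The SAP Introduction says the SAP is "based on the Clinical Investigation Plan (CIP) version 4 dated July 29, 2022". SAP 7.12 adds: "This version of the SAP is updated to reflect changes in the CIP from version 3 to version 4". It continues: "There have been no direct changes in the proposed analyses of study objectives". It mentions neither difference.

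**The concern.** Both texts are current, and nothing in either reconciles them. Who enters the 70/10/20 training, validation and test split, and from which day each patient contributes windows, depends on which document the analyst opens.

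The survey condition is not the rule that patients must supply minimal HCU information. CIP 13.2 and SAP 7.2 say that rule is met by monthly and triggered surveys or by EHR sharing. The HCU survey is not a baseline task; it starts 30 days after enrollment or at the first triggered event. EQ-5D-5L and AFEQT are not needed to determine the endpoint, since site personnel confirm HCU through the EHR (Addendum 5.1).

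Under the SAP, a patient who never finishes a baseline questionnaire has no time zero and leaves the primary analysis, and events between consent and task completion fall before follow-up begins. The remaining patients may be the more engaged ones, although the documents give no data on this. The exclusion could also go unseen: the flow diagram in SAP 7.1.1 counts patients with at least one survey and those with 75% of tasks done, but not those who completed the enrollment surveys.

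**Working it through.** **1. The texts side by side**

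| Rule | CIP v4 | SAP |
|---|---|---|
| Primary population | 13.3.2: enrolled, app installed, consented | 7.9.1: full analysis set and all enrollment surveys completed |
| Start of follow-up, enrolled or tasks finished more than 7 days after implant | 13.2: electronic consent | 7.2: all baseline tasks complete |

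The SAP's full analysis set matches the CIP population, so the survey condition enters only at SAP 7.9.1. As supporting evidence of intent, the CIP version history records that v4 removed this requirement from section 13.3.2. The conflict does not depend on that entry.

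**2. The plan's own figures** (CIP 13.1, SAP 6)

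- AF-related events: 5,000 × 0.21 = 1,050. With complete data from 50% of the cohort: 1,050 × 0.50 = 525. Both reproduce.
- Minimum events for predictor influence: 80/0.05/10 = 160 and 80/0.02/10 = 400. The stated minimum for a prediction algorithm, 320 to 800, is twice these.
- Follow-up per patient: 5,200,000 / 5,000 = 1,040 days.

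**3. Population effect, illustration only**

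Let c be the fraction completing all enrollment surveys. The documents give no value. Assume c is independent of events and of the 50% data loss already discounted. Events = 525 × c; test-set events = 525 × c × 0.20.

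| c | Events | Test set (20%) |
|---|---|---|
| 1.0 (CIP population) | 525 | 105 |
| 0.9 | 472.5 | 94.5 |
| 0.8 | 420 | 84 |
| 0.7 | 367.5 | 73.5 |

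The total falls below the 320-event minimum when c < 320/525 = 0.61.

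**4. Time-zero effect for later enrollees**

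A delay of d days costs d/1,040 of the implied follow-up: 7 days 0.7%, 14 days 1.3%, 30 days 2.9%.

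SAP Table 1 gives the re-issue and expiry windows. Suppose the baseline form lapses and the next issue counts as completion:

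- AFEQT: re-issued at day 30 ± 2, open 14 days. Completion falls on day 28 to 32 + 14 = 46, a delay of 28/1,040 = 2.7% to 46/1,040 = 4.4%.
- EQ-5D-5L: re-issued at day 90 ± 2, open 30 days. Completion falls on day 88 to 92 + 30 = 122, a delay of 88/1,040 = 8.5% to 122/1,040 = 11.7%.

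If the next issue does not count, the patient is excluded. The text available does not say which applies. Medication history is a baseline task with no expiration, so the delay has no overall cap.

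**The case against.** The strongest reply is that the SAP may restrict. SAP 7.1.3 allows objective-specific constraints, and CIP 13.2 makes each analysis depend on data completeness. CIP 13 leaves missing data to the SAP and allows non-principal changes to be justified in the study report. A modelling reason is also visible: the enrollment surveys include medical and medication history, and CIP 13.3.1 lets the model use medical history given at enrollment. This shows that a restriction could be legitimate. It does not show that this one was chosen. SAP 7.9.1 gives no reason, SAP 7.12 records no departure, and patient history is already required for enrollment. In practice the condition therefore bites mainly on medication history, EQ-5D-5L and AFEQT.

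Several points on size do stand:

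- The completion rates above are assumed. Patients who skip surveys may overlap with the 50% already discounted, in which case the table overstates the loss.
- The 61% threshold uses the low end of the 320 to 800 range; 525 is already below the high end.
- Predictions in the test set begin only at day b, which is not yet set, so some early days may yield no prediction under either rule.
- The lapse delays describe particular patients, with no frequency known.
- No hypothesis is tested, and no changed conclusion has been shown.

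SAP 7.12 also does not assert in terms that the two documents agree; it simply does not disclose the differences. None of this reconciles the two rules.

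**Conclusion.** The concern holds. The SAP contradicts the CIP version it says it is based on, both on the primary population and on the start of follow-up for later enrollees. This rests on the current wording alone and needs no numerical assumption. It must be settled before modelling, because it fixes who is split and which days count.

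The size of the loss is unknown. Under the stated independence assumptions, completion of 70% to 90% would remove about 53 to 158 of 525 AF-related events (525 − 472.5 and 525 − 367.5), and the 320-event minimum would fail only below about 61% completion. Selection on engagement is possible but not demonstrated.

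**What to change.** - **SAP 7.9.1:** replace the population sentence with the CIP 13.3.2 population. Keep the exclusion of ineligible patients (CIP 9.11, SAP 7.1.2) and the device-data and minimal-HCU conditions of CIP 13.2 and SAP 7.2.
- **SAP 7.2:** start follow-up for later enrollees at electronic consent, as in CIP 13.2.
- **SAP 7.12:** record both alignments.
- **Missing questionnaires:** treat an absent baseline questionnaire as a missing feature under the missing-data provision of SAP 7.9.1. Say so expressly, so that the default in SAP 7.4 of leaving out data points with missing values does not bring the exclusion back.
- **Optional:** keep survey completers as a sensitivity set. State whether a re-issued AFEQT or EQ-5D-5L counts as baseline completion, and whether models are retrained or only re-evaluated in that set.

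The cost is two SAP sentences, one line in SAP 7.12, a clarifying phrase on missing features and, if wanted, one sensitivity analysis. No protocol amendment and no new data are needed. If the sponsor does intend the restriction, it should state and justify it as a departure from CIP v4 and decide whether it changes a principal feature of the CIP, which by CIP section 13 would call for an amendment.

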7.10 Safety Evaluation

Summary and listing of any deaths will be reported.

7.11 Health Outcomes Analyses

[figure not shown]
None

7.12 Changes to Planned Analysis

This version of the SAP is updated to reflect changes in the CIP from version 3 to version 4. Most of the CIP changes had to do with clarifications around the deployment of patient surveys, which have also been updated in this SAP. Changes in the inclusion criteria and descriptions of study objectives have

Revision [2.0]

Page 24 of 25

also been updated in this SAP. There have been no direct changes in the proposed analyses of study objectives. There was a delay in the timing of the interim analysis, which is discussed in Section 7.8.

8. Validation Requirements

All programs written to execute the analyses in this SAP will pass through at least Level II validation

9. References

- 2. Catling, F.J.R., & Wolff, A. H. (2020). Temporal convolutional networks allows early prediction of events in critical care. *Journal of the American Medical Informatics Association*, 27(3), 355-365

DEFINE AFib Statistical Analysis Plan Form Medtronic Revision [2.0] Page 25 of 25
